### **Reasons for SVR12 Non-Response**

Subjects who do not achieve SVR12 (SVR12 non-responders) will be categorized as having:

1. On-treatment HCV virologic failure (see **On-treatment HCV virologic failure** definition; if a subject meets both definitions of **Breakthrough** and **EOT failure**, he or she will be categorized as **Breakthrough** only);
2. Relapse12;
3. Prematurely discontinued study drug with no on-treatment HCV virologic failure (defined as any SVR12 non-responder who prematurely discontinued study drug [study drug duration < 77 days for subjects assigned to 12 weeks of treatment, and < 105 days for subjects assigned to 16 weeks of treatment] and did not meet the **On-treatment HCV virologic failure** definition);
4. HCV reinfection (see definition described earlier) ;
5. Missing follow-up data in the SVR12 window (defined as any subject who completed study drug without data in the SVR12 window after applying the imputation rules and not meeting the definitions of [1], [2], [3], or [4]);
6. Other (defined as any SVR12 non-responder not meeting the definitions of [1] – [5]).

#### **Reasons for SVR24 Non-Response**

Subjects who do not achieve SVR24 (SVR24 non-responders) will be categorized as having:

1. On-treatment HCV virologic failure (see **On-treatment HCV virologic failure** definition; if a subject meets both definitions of **Breakthrough** and **EOT failure**, he or she will be categorized as **Breakthrough** only);
2. Relapse12;
3. Relapse24;
4. Prematurely discontinued study drug with no on-treatment virologic failure (defined as any SVR24 non-responder who prematurely discontinued study drug [study drug duration < 77 days for subjects assigned to 12 weeks of treatment, and

< 105 days for subjects assigned to 16 weeks of treatment] and did not meet the **On-treatment HCV virologic failure** or **Relapse24** definitions);

5. HCV reinfection (see definition described earlier);
6. Missing follow-up data in the SVR24 window (defined as any subject who completed study drug without data in the SVR24 window after applying the imputation rules and not meeting the definitions of [1], [2], [3], [4], or [5]);
7. Other (defined as any SVR24 non-responder not meeting the definitions of [1] – [6]).

For the reasons for SVR12 and SVR24 nonresponse defined above, subjects are only to be counted in 1 category. For example, the categories of premature discontinuation and reinfection are mutually exclusive. Thus, subjects who are SVR12 or SVR24 nonresponders meeting the definition of HCV reinfection will be counted in the reinfection category and will not be counted in any other category (as in the example, even if such a subject appears to meet the definition of prematurely discontinued study drug with no on-treatment HCV virologic failure, the subject would be counted in the reinfection category only).

## **10.2 Handling of Multiplicity**

There will be no hypothesis testing for the primary and secondary efficacy endpoints. Therefore, there will be no adjustment for multiple comparisons.

## **10.3 Primary Efficacy Analysis**

The primary efficacy endpoint is SVR12 (HCV RNA < LLOQ 12 weeks after the last actual dose of study drug). The number and percentage of subjects in the ITT population achieving SVR12 will be summarized with a two-sided 95% CI, calculated using the normal approximation to the binomial distribution. If the SVR12 rate is 100%, then the Wilson's score method will be used to calculate the confidence interval. No hypothesis will be tested.

## 10.4 Secondary Efficacy Analyses

The secondary efficacy endpoints are:

- the percentage of subjects with on-treatment HCV virologic failure (defined as **On-treatment HCV virologic failure**);
- the percentage of subjects with post-treatment relapse (defined as **Relapse12**; subjects with reinfection will be summarized separately);
- the percentage of HCV/HIV co-infected subjects (determined at Screening) achieving SVR12.

The numbers and percentages of subjects with on-treatment HCV virologic failure, post-treatment relapse (**Relapse12**), and SVR12 will be calculated along with two-sided 95% Wilson score CIs.

In addition, a summary of reasons for SVR12 non-response (e.g., on-treatment HCV virologic failure, relapse, re-infection, other) will be provided for the set of all subjects and for the set of HCV/HIV co-infected subjects. Listings of subject numbers with reason for non-response will be prepared.

## 10.5 Sensitivity Analyses for SVR12

Two-sided 95% CIs for the primary endpoint SVR12 rate will be calculated using both the normal approximation to the binomial distribution and the Wilson score method.

Analyses of the primary endpoint will also be performed on the mITT-GT and mITT-GT-VF populations. Both two-sided 95% normal approximation and Wilson score CIs will be provided for each of these sensitivity analyses.

The analyses described above will also be performed for the geographic region of China.

For each sensitivity analysis, a two-sided 95% CI will be produced only if there are at least 10 subjects in the summary.

Listings of subjects excluded from the mITT-GT and mITT-GT-VF populations will be provided, as applicable.

### **10.5.1 Imputation Approaches**

In addition to imputing SVR12 as described in Section 6.3, SVR12 in the ITT population will be presented using the following other methods to impute missing HCV RNA values:

- impute any missing HCV RNA values in the SVR12 window by carrying forward the last non-missing (post-baseline) HCV RNA value prior to the SVR12 window;
- impute as described in Section 6.3 but treat SVR12 non-responders who were categorized as "prematurely discontinued study drug with no on-treatment virologic failure" or "missing follow-up data in the SVR12 window" as successes.

For each of these, the number and percentage of subjects with SVR12 will be presented along with two-sided 95% CIs using both the normal approximation to the binomial distribution and the Wilson score method. These analyses will be performed for the set of all subjects and for the geographic region of China.

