#### **5.1.2 Modified Intention-to-Treat (mITT) Populations**

Sensitivity analyses of SVR12 as described in Section 10.5, when applicable, will be performed on the ITT population modified to exclude subjects of multiple genotypes according to the central laboratory or phylogenetic analyses or subjects who received incorrect duration of treatment due to incorrect classification of GT or treatment experience at screening (mITT-GT), and on the mITT-GT population modified to exclude subjects who did not achieve SVR12 for reasons other than virologic failure (i.e., subjects with reasons other than on-treatment HCV virologic failure and relapse) (mITT-GT-VF).

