### **Definitions for Efficacy Endpoints**

A confirmed quantifiable value during treatment is defined as any two consecutive HCV RNA measurements  $\geq$  LLOQ (or 100 IU/mL for **Breakthrough**), either both during treatment or at the final treatment measurement and the next consecutive post-treatment measurement. A confirmed quantifiable post-treatment value is defined as any two consecutive post-treatment HCV RNA measurements  $\geq$  LLOQ.

**Breakthrough** = confirmed HCV RNA  $\geq$  100 IU/mL after HCV RNA < LLOQ during the Treatment Period; or confirmed increase from nadir in HCV RNA (two consecutive HCV RNA measurements > 1 log10 IU/mL above nadir) at any time point during the Treatment Period. A single breakthrough value ( $\geq$  100 IU/mL or > 1 log10 above nadir) followed by lost to follow-up also will be considered a breakthrough (i.e., will not require confirmation).

**EOT failure** = HCV RNA  $\geq$  LLOQ at end of treatment with at least 6 weeks of treatment, where the HCV RNA value must be collected on or after Study Drug Day 36 and study drug duration  $\geq$  36 days.

**On-treatment HCV virologic failure** = **Breakthrough** or **EOT failure**; if a subject meets both definitions of **Breakthrough** and **EOT failure**, he or she will be categorized as **Breakthrough** only.

**SVR4** = HCV RNA  $<$  LLOQ in the SVR4 window (4 weeks after the last actual dose of study drug) without any confirmed quantifiable ( $\geq$  LLOQ) post-treatment value before or during that SVR window.

**SVR12** = HCV RNA  $<$  LLOQ in the SVR12 window (12 weeks after the last actual dose of study drug) without any confirmed quantifiable ( $\geq$  LLOQ) post-treatment value before or during that SVR window.

**SVR24** = HCV RNA  $<$  LLOQ in the SVR24 window (24 weeks after the last actual dose of study drug) without any confirmed quantifiable ( $\geq$  LLOQ) post-treatment value before or during that SVR window.

**Relapse12** = confirmed HCV RNA  $\geq$  LLOQ between end of treatment and 12 weeks after last actual dose of study drug (up to and including the SVR12 assessment time point) for a subject with HCV RNA  $<$  LLOQ at Final Treatment Visit who completed treatment and has post-treatment HCV RNA data available, excluding reinfection as described below.

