## **10.7 Additional Efficacy Analyses**

The ITT population will be used to summarize the following additional efficacy endpoints for the set of all subjects and for the geographic region of China:

- The percentage of subjects with HCV RNA < LLOQ at each post-baseline visit in the Treatment Period (using data as observed);
- The percentage of subjects with SVR4;
- A summary of reasons for SVR4 non-response (e.g., on-treatment virologic failure, relapse, re-infection, other);
- The percentage of subjects with HCV virologic failure through PT Week 12 (i.e., the SVR12 non-responders due to on-treatment virologic failure or Relapse12);
- The percentage of subjects with SVR24\*;
- A summary of reasons for SVR24 non-response (e.g., on-treatment virologic failure, relapse, re-infection, other)\*;

- The percentage of subjects who relapsed after achieving SVR12 (**Relapse24**).

\* These endpoints will be summarized for the HCV/HIV co-infected subjects (determined at Screening) within the populations/groups identified above.

In the above analyses for SVR, HCV virologic failure, and relapse, the number and percentage of subjects along with a two-sided 95% Wilson score CI will be calculated. Imputations for missing data will be performed as described in Section 6.3 for analysis of SVR, HCV virologic failure, and relapse. All other endpoints will be presented using data as observed.

As additional endpoints, the secondary endpoints will be summarized for the geographic region of China. A summary of the subjects who completed treatment and relapsed (defined as **Relapseoverall**) will be prepared displaying the number of subjects relapsing overall and by SVR visit window (within the SVR4, SVR12, SVR24 windows or after SVR24 window), including the subject number and the SVR visit window corresponding to the first HCV RNA value of those indicating the occurrence of relapse. A similar listing will be prepared for subjects who prematurely discontinued treatment and relapsed after having HCV RNA < LLOQ at their Final Treatment Visit. These summaries will be performed for the overall ITT population and for the geographic region of China within the ITT population.

Listings of subject numbers with reason for non-response will be prepared for the SVR endpoints.

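### The second SVR12 imputation in SAP 10.5.1 counts early stoppers with observed post-treatment viraemia as cured, although the section is meant to impute missing values

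*SAP*

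**What the plan says.** SAP 10.5.1 states that SVR12 in the ITT population "will be presented using the following other methods to impute missing HCV RNA values". Two methods follow. The first fills an empty SVR12 window "by carrying forward the last non-missing (post-baseline) HCV RNA value prior to the" window. The second applies Section 6.3, then treats as successes the "non-responders who were categorized as 'prematurely discontinued study drug with no on-treatment virologic failure' or" as having no follow-up data in the SVR12 window. Both are reported for all subjects and for China.

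The categories come from SAP 10.1:

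- **Relapse12** needs confirmed HCV RNA at or above LLOQ after treatment, in a subject below LLOQ at the Final Treatment Visit "who completed treatment and has post-treatment HCV RNA data available, excluding reinfection as described below". Completion means at least 77 days of drug (12-week assignment) or 105 days (16-week assignment).
- **EOT failure** needs a quantifiable value on or after day 36 and at least 36 days of drug.
- **Category 3**, premature discontinuation, takes any SVR12 non-responder below the 77- or 105-day threshold "and did not meet the On-treatment HCV virologic failure definition". Post-treatment HCV RNA plays no part.
- **Reinfection** takes precedence: a reinfected non-responder is counted there and nowhere else.

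SAP 10.7 plans a listing of "subjects who prematurely discontinued treatment and relapsed after having HCV RNA < LLOQ" at the Final Treatment Visit.

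**The concern.** Setting missing outcomes to success is a legitimate favourable bound. It pairs naturally with Section 6.3, which sets them to failure. The second method goes further, because its unit is a reason category and not a missing value. A subject who stops at day 60 while suppressed and is then quantifiable at Post-Treatment Weeks 4 and 12 has a known outcome, yet the method reports that subject as SVR12.

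The plan foresees such subjects. Besides the SAP 10.7 listing, SAP 10.8 provides for sequencing samples from premature discontinuers without on-treatment failure who have HCV RNA of 1000 IU/mL or more after stopping (South Korea, and GT1 in China). One plan could therefore sequence a subject's post-treatment virus and count the same subject as cured. All treated subjects are followed for 24 weeks, so these values will normally exist.

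At stake is what the figure means. A reader will take it as the effect of missing data on SVR12, when it may also contain reversed failures, always in the favourable direction.

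**Working it through.** **1. The plan's own interval.** SAP 4.3 assumes 95% of 160, that is 152/160. The normal approximation gives 0.95 ± 1.96 × √(0.95 × 0.05 / 160) = 0.95 ± 0.0338, or 91.62% to 98.38%. This matches the stated 91.6% to 98.4%, so the same formula is used below.

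**2. Classification.** Test subjects assigned to 12 weeks were run through the SAP 10.1 definitions and then the second method. The last column applies the condition proposed under the fix.

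| Test subject | SAP 10.1 reason | Second method as written | With the condition |
|---|---|---|---|
| Completer, < LLOQ at last dose, confirmed post-treatment viraemia | Relapse12 | failure | failure |
| Stops day 60, < LLOQ at last dose, confirmed post-treatment viraemia | premature discontinuation | **success** | failure |
| Stops day 20, still ≥ LLOQ at last dose without breakthrough, viraemic at PT Week 12 | premature discontinuation | **success** | failure |
| Stops day 60, < LLOQ at last dose, no post-treatment data | premature discontinuation | success | success |
| Stops day 60, reinfection | reinfection | failure | failure |
| Stops day 60, EOT failure | on-treatment virologic failure | failure | failure |

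Rows 2 and 3 are the fault. Row 2 arises because relapse is restricted to completers. Row 3 arises because stopping before day 36 rules out EOT failure. Row 4 is the case the method can properly serve.

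**3. Effect per subject.** 1/160 = 0.625 points overall. The planned China enrolment is 60 + 36 + 24 = 120, so 1/120 = 0.83 points there.

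**4. Illustration.** The documents give no count, so the split is assumed: 152/160 respond; 3 of the 8 non-responders have no value in the window and meet the proposed condition; v are viraemic early stoppers. With the condition the result does not depend on v: (152 + 3)/160 = 155/160. As written it is (155 + v)/160.

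| v | As written | Normal approx. 95% CI | Wilson 95% CI |
|---|---|---|---|
| 0 (equals the corrected result) | 155/160 = 96.9% | 94.2 to 99.6 | 92.9 to 98.7 |
| 1 | 156/160 = 97.5% | 95.1 to 99.9 | 93.8 to 99.0 |
| 2 | 157/160 = 98.1% | 96.0 to 100.2 | 94.6 to 99.4 |
| 3 | 158/160 = 98.75% | 97.0 to 100.5 | 95.6 to 99.7 |

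**5. Rough scale.** Protocol Tables 6 and 8, subjects with cirrhosis:

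- N = 101 + 35 + 20 + 2 + 7 + 65 + 51 = 281.
- SVR12 = 98 + 35 + 20 + 2 + 7 + 64 + 48 = 274.
- Virologic failures: one GT1 relapse, plus one on-treatment failure and two relapses in treatment-experienced GT3, giving 4.
- Other non-responders: 281 − 274 − 4 = 3, or 1.07%. Per 160 subjects, 160 × 3/281 = 1.7.

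**The case against.** The strongest defence is that little depends on this analysis. No hypothesis is tested, and the method is one supplementary presentation added to match the wider program (SAP 12.1). A favourable bound is meant to be favourable, and Section 6.3 already supplies the unfavourable one. The lead-in speaks of missing values, so the authors may have had only those in mind. The affected subjects are also visible in the listings of reasons for non-response (SAP 10.4) and of relapse after early discontinuation (SAP 10.7).

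The limits on reach and size stand. The rest does not remove the fault. The rule as written acts on the whole category whatever the lead-in intends. A listing shows a reader who was reclassified but leaves the reported rate wrong. A bound on unknown outcomes gives no reason to overwrite known ones.

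Two wider inferences are tempting:

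- **Carry-forward.** The first method also favours success, because it can carry an on-treatment suppressed value into the window. It fills only empty windows, though, and SVR12 still requires no confirmed quantifiable post-treatment value. It reverses no observed value in the window, so objecting to it is a preference about method.
- **mITT-GT-VF.** This population drops the same early stoppers, since it excludes those without SVR12 "for reasons other than virologic failure (i.e., subjects with reasons other than on-treatment HCV virologic failure and relapse"). The exclusion is stated openly, the population is defined in Protocol 8.1, and it feeds the regression in SAP 10.6 and the polymorphism analyses in SAP 10.8. Simply restoring viraemic early stoppers would also bring reinfected subjects back in unless they were carved out.

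**Conclusion.** The point holds for the second method of SAP 10.5.1. As written, it turns observed post-treatment failures among early stoppers into SVR12 successes. Early stoppers who meet reinfection or on-treatment virologic failure remain failures.

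Each affected subject adds 0.63 points to the sensitivity estimate at n=160, or 0.83 at China n=120, assuming enrolment as planned. The number affected is unknown and may be zero. The 1.7 per 160 is only a rough scale: it covers all non-virologic non-response, and the tables do not show that any of the three subjects was viraemic. Protocol 3.0 also reports no treatment discontinuations among 82 subjects with cirrhosis who had at least 4 weeks of treatment.

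A reader might infer that the headline SVR12 is inflated, or that a large share of expected failures would disappear. The documents support neither. These subjects remain failures in the primary analysis, and no source in the documents counts viraemic early stoppers.

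**What to change.** In the second method of SAP 10.5.1, treat a non-responder in category 3 (premature discontinuation) or category 5 (missing follow-up) as a success only if all three conditions hold:

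1. there is no HCV RNA value in the SVR12 window after the Section 6.3 imputations;
2. there is no confirmed post-treatment HCV RNA at or above LLOQ, where a last available post-treatment value at or above LLOQ counts without confirmation, as SAP 10.1 already provides for relapse;
3. the last available HCV RNA value is below LLOQ.

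All other subjects in these two categories stay failures. The third condition also keeps as a failure an early stopper who is lost while still quantifiable on treatment.

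The cost is one clause in the SAP and one programming condition, applied to the overall and China summaries alike. No new data are needed. The primary analysis, the carry-forward method and the analysis populations stay as they are.

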8.0 Statistical Methods and Determination of Sample Size

8.1 Statistical and Analytical Plans

The primary analysis will occur after all subjects have completed the PT Week 12 Visit or prematurely discontinued the study. The data for the primary analysis will be locked after

data cleaning. Data collected after this lock will be added to a new version of the database which will be cleaned and locked at the end of the study.

SAS[®] (SAS Institute, Inc., Cary, NC) for the UNIX operating system will be used for all analyses. All statistical tests and confidence intervals will be two-sided with an alpha level of 0.05. Descriptive statistics will be provided, such as the number of observations (N), mean, and standard deviation (SD) for continuous variables and counts and percentages for categorical variables.

Data across subjects of all genotypes will be combined for analysis, unless otherwise indicated. Analyses will be performed on the intent-to-treat (ITT) population defined as all enrolled subjects who receive at least one dose of study drug, unless otherwise specified. Sensitivity analyses of the primary efficacy endpoint, when applicable, will be performed on the ITT population modified to exclude subjects of multiple genotypes according to the central laboratory or phylogenetic analyses (mITT-GT), and on the mITT-GT population modified to exclude subjects who did not achieve SVR₁₂ for reasons other than virologic failure (mITT-GT-VF).

No data will be imputed for any efficacy or safety analysis except for analyses of SVR endpoints (HCV RNA data) and PRO questionnaires. HCV RNA values will be selected for the analyses of all SVR endpoints (e.g., SVR₄, SVR₁₂, and SVR₂₄) based on defined visit windows. A backward imputation method will be used to impute missing responses for SVR analyses. Imputation of missing responses on PRO questionnaires is described in Section 8.1.3.

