### **4.3 Sample Size**

It is planned to enroll approximately 160 subjects. The sample size for this study is driven by the expected sample size requirements for each genotype and geographical region for this secondary indication. No formal hypothesis is being tested in this study. If the observed SVR12 rate in this study is 95% among 160 subjects, then the two-sided 95% confidence interval (CI) calculated using the normal approximation for a single binomial proportion is 91.6% to 98.4%.

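### The second imputation analysis in SAP 10.5.1 counts early stoppers with observed post-treatment viraemia as SVR12 successes, although it is presented as a way to handle missing data

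*SAP*

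**What the plan says.** SAP 10.5.1 adds two presentations of SVR12 in the ITT population, "using the following other methods to impute missing HCV RNA values". The first carries forward the last post-baseline value before the SVR12 window. The second applies Section 6.3 and then counts as successes those non-responders "who were categorized as 'prematurely discontinued study drug with no on-treatment virologic failure' or 'missing follow-up data in the" SVR12 window. Both are reported as a number and percentage with normal-approximation and Wilson 95% intervals, overall and for China.

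The two relabelled groups are categories 3 and 5 of the reasons for SVR12 non-response in SAP 10.1. Category 3 takes any non-responder who stopped early ("study drug duration < 77 days for subjects assigned to 12 weeks of treatment, and < 105 days for subjects assigned" to 16 weeks) without on-treatment virologic failure. Category 5 takes subjects who completed drug and have no window value after imputation.

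Relapse12 applies only to a subject below LLOQ "at Final Treatment Visit who completed treatment and has post-treatment HCV RNA data available, excluding reinfection as described below". End-of-treatment failure needs a drug duration of at least 36 days and a quantifiable value on or after Day 36.

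SAP 10.7 plans a listing of relapses among completers and adds: "A similar listing will be prepared for subjects who prematurely discontinued treatment and relapsed" after being below LLOQ at the Final Treatment Visit.

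**The concern.** An imputation rule should act only where the outcome is unknown. Category 5 meets that condition. Category 3 does not, because it sorts subjects by how long they took the drug and not by whether HCV RNA was measured afterwards. A subject who stopped early, was followed and was found viraemic has a known outcome. The second bullet replaces that outcome with its opposite.

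The result would appear as an ITT SVR12 rate with intervals and no label marking it as a best case. A reader would take it as a check on missing data, when part of any gain over the primary rate could come from overwritten failures. The same report could list a subject under SAP 10.7 as having relapsed and count that subject as SVR12 under 10.5.1.

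**Working it through.** **1. The plan's own figure.** SAP 4.3 states that if the "rate in this study is 95% among 160 subjects, then the two-sided 95% confidence interval (CI) calculated using the normal approximation" gives 91.6% to 98.4%. With p = 152/160 = 0.95, the standard error is sqrt(0.95 × 0.05 / 160) = 0.01723. The interval is 0.95 ± 1.96 × 0.01723, or 91.62% to 98.38%, so the figure is reproduced. Section 10.5.1 gives no figure of its own.

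**2. Tracing subjects through SAP 6.3, 10.1 and 10.5.1.**

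| Subject | Category in 10.1 | Primary | Second bullet | Outcome observed? |
|---|---|---|---|---|
| Stops on Day 76 of a 12-week course below LLOQ; quantifiable at PT Weeks 4 and 12 | 3 (not a completer, so not Relapse12) | Failure | Success | Yes |
| Stops on Day 20 still viraemic, no breakthrough, no later clearance | 3 (under 36 days, so not end-of-treatment failure) | Failure | Success | Yes |
| Stops on Day 50, quantifiable at that visit | 1 (end-of-treatment failure) | Failure | Failure | Yes |
| Completes, then rebounds with the same virus | 2 (Relapse12) | Failure | Failure | Yes |
| Completes, below LLOQ when last seen, no window value | 5 | Failure | Success | No |

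The first two rows are the defect. A category 3 subject with a retained value in the SVR12 window can be a non-responder only through quantifiable HCV RNA, so nothing is being imputed. Category 5 is largely free of the problem: under SAP 10.1 a completer whose last post-treatment value is at or above LLOQ already counts as a relapse without confirmation.

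**3. Size per subject.** At N = 160, 100/160 = 0.625 points. For China the planned numbers are 60 + 36 + 24 = 120, and 100/120 = 0.83 points.

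**4. Range.** The documents give no counts for categories 3 and 5. Assume 152/160 in the primary analysis, so 8 non-responders, with k of them in these two categories.

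| k relabelled | Reported rate | 95% interval |
|---|---|---|
| 0 | 152/160 = 95.0% | 91.6 to 98.4 (normal) |
| 1 | 153/160 = 95.6% | 92.5 to 98.8 (normal) |
| 2 | 154/160 = 96.25% | 93.3 to 99.2 (normal) |
| 4 | 156/160 = 97.5% | 95.1 to 99.9 (normal) |
| 8 | 160/160 = 100% | 97.7 to 100 (Wilson) |

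Only the viraemic part of k is in error. If k = 2 and one of the two is viraemic (an assumption), the bullet reports 96.25% where 95.6% would be right.

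**5. A plausible ceiling.** The cirrhosis rows of Protocol Tables 6 and 8 sum as follows:
- Subjects: 101 + 35 + 20 + 2 + 7 + 65 + 51 = 281.
- SVR12: 98 + 35 + 20 + 2 + 7 + 64 + 48 = 274, so 7 non-responders.
- Virologic failures: 1 GT1 relapse, plus 1 on-treatment failure and 2 relapses in treatment-experienced GT3 = 4. This leaves 3 others.

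Scaled to this trial, 3/281 × 160 = 1.7 subjects, or about 1.1 points if all were relabelled (274/281 = 97.5% becomes 277/281 = 98.6%). That covers non-virologic non-response of every kind. The tables do not say how many, if any, were early stoppers with measured viraemia.

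**The case against.** The strongest reply is that this is a sensitivity analysis, nothing is tested, and the primary analysis already treats missing as failure. A deliberately generous counterpart is legitimate, and an upward direction is what an upper bound has. This stands for subjects whose outcome is unknown. It does not cover subjects whose failure was measured, and the SAP does not call the result a bound.

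It can also be said that the first bullet already confines itself to missing values, and that the planned listings of reasons for non-response let a reader find the relabelled subjects. Both are true and both limit the harm. Neither corrects the rate that will be printed.

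The number affected may be nil. Protocol 3.0 reports no treatment discontinuations among 82 cirrhotic subjects with at least 4 weeks of treatment in the Phase 2 arms.

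Three stronger readings are tempting and are not supported:
- **Every death becomes a success.** Deaths with on-treatment failure, Relapse12 or reinfection stay failures. A death without a window value is genuinely missing HCV RNA, which a best-case bound may include if it says so.
- **Every re-treated subject becomes a success.** Section 6.3 makes such subjects failures whatever imputation is used there. The second bullet starts from 6.3 and then makes exceptions. The SAP does not say which rule prevails, so this is an unresolved conflict.
- **The definition of mITT-GT-VF is part of the same error.** That population drops non-responders for non-virologic causes ("i.e., subjects with reasons other than on-treatment HCV virologic failure and relapse"). Protocol 8.1 already defines it that way, so it is a separate question.

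**Conclusion.** The point holds for one sensitivity analysis. As written, the second bullet of SAP 10.5.1 reports as SVR12 successes early stoppers whose post-treatment viraemia was observed, and no other part of the SAP prevents it. The error can only raise the rate, by 0.625 points per subject overall and about 0.83 in China. The count of such subjects is unknown and may be zero; the 1.7 per 160 derived above is a rough ceiling from other studies and assumes that all three of their non-virologic non-responders would fall in categories 3 or 5. A reader might infer that the primary SVR12 result is inflated. It is not: it counts all these subjects as failures. Severity is minor to moderate, and the case for correction rests on validity more than on size.

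**What to change.** Reword the second bullet of SAP 10.5.1:
- Relabel as successes only category 3 or 5 subjects who have no HCV RNA value in the SVR12 window after Section 6.3 and whose last available value is not at or above LLOQ.
- Keep subjects with observed quantifiable post-treatment HCV RNA as failures.
- State that the Section 6.3 rule of failure after new HCV therapy still applies, which removes the present conflict.
- Label the result a best-case bound and say how deaths are counted.
- Report the number relabelled, overall and for China.

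The cost is a few lines of SAP text and one programming filter, with no new data. The reworded bullet comes close to the first one (last value carried forward), differing mainly in how deaths and re-treated subjects are handled. The sponsor should accept that overlap knowingly. The sensitivity rate may come out slightly lower.
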